1.2.4 BMS-986253

1.2.4.1 Background and safety

BMS-986253 (HuMax-Immune) is a fully human IgG1 kappa neutralizing monoclonal antibody against IL-8. It binds the IL-8 epitope on both IL-8 isoforms (72 and 78 amino acids), important for CXCR1/2 binding, and prevents IL-8 from binding to its corresponding receptors. Since BMS-986253 cannot bind receptor-bound IL-8, it shows no antibody dependent cell-mediated cytotoxicity (ADCC) or complement-dependent cytotoxicity (CDC). It shows no cross-reactivity with other human tissues or chemokines.[\[95\]](#)

BMS-986253 has been tested in a single dose PK study in monkeys at 20 and 160 mg/kg. The dosing was clinically tolerable in the monkeys. A reduction of serum IL-8 to below the lower limit of detection was seen for the total follow-up period of 6 weeks. A larger multiple dose toxicokinetic study in cynomolgus monkeys at doses 20, 80 and 160 mg/kg/week for 12 weeks has been completed and showed no safety issues.

A phase I/II clinical trial[\[96\]](#) designed to evaluate safety and efficacy in palmoplantar pustulosis (PPP), a rare chronic inflammatory skin disorder, enrolled 31 participants. For PPP, BMS-986253 showed efficacy in reducing disease activity. The antibody was well-tolerated, with no serious adverse events (SAE) attributed to treatment. The most frequently reported mild or moderate adverse events included nausea, nasopharyngitis, and headache. Moreover, no antihuman antibodies developed after administration of BMS-986253.[\[96\]](#) In the phase I trial of BMS-986253 in advanced solid tumors as monotherapy,[\[97\]](#) 11/15 subjects achieved the best response of stable disease (4 subjects had progressive disease). Reduction of serum IL-8 levels were observed across all dose levels (4, 8, 16 and 32 mg/kg every 2 weeks) without reaching a dose-limiting toxicity (DLT) or defining maximum tolerated dose (MTD). Treatment with BMS-986253 reversed EMT process measured by the EMT markers and inhibited IL-8 induced peripheral blood cells migration isolated from subjects post-treatment. The most common

adverse events (AE), regardless of causality, were constipation (n=5), nausea (n=4) and anemia (n=4). Six subjects (40%) had grade 3 AEs with increased ALP (n=2) and anemia (n=2) being the most common. Treatment-related AEs occurred in one-third of the subjects and were all grade 1 and 2 (anemia and fatigue as the most common). Four subjects experienced SAE non-related to the treatment (grade 3 pain, abdominal infection, fall, decreased ALP, hyponatremia [n=5]; grade 2 pulmonary embolism [n=1]). The pharmacokinetic (PK) analysis showed an approximate linear correlation between increasing dose and exposure for the dose range of 4 mg/kg to 32 mg/kg.[\[97\]](#)

In the currently ongoing clinical trial phase 1/2 (CA027-002, ClinicalTrials.gov [NCT03400332](#)), testing various flat doses of BMS-986253 in combination with nivolumab, treatment-related AEs were observed in 140/144 participants with solid cancer at the time of the preliminary analysis (data cutoff date of 16-Jan-2023). No DLTs were observed, and no safety signals were identified. The most common treatment-related AEs in combination with nivolumab were fatigue (n=53), malignant neoplasm progression (n=44), nausea and anemia (n=35), and decreased appetite (n=33), dyspnea and diarrhea (n=29), constipation (n = 27), pyrexia (n = 24), abdominal pain (n = 19), asthenia and weight decreased (n = 18), urinary tract infection, pneumonia, vomiting, hyponatremia, and arthralgia (n = 17), pruritus (n = 16), and cough (n = 15). Other Grade 5 AEs include sepsis, respiratory failure, cardiac death, death, pneumonia, pneumonia aspiration, neoplasm malignant, neoplasm progression, arterial rupture, and cardiac arrest (n = 1).Based on preliminary clinical data from that trial BMS-986253 does not appear to significantly increase the rate of nivolumab-induced AEs.[\[95\]](#)

Based on currently available clinical data from prior trials including 158 participants,[\[95-97\]](#) only 3 participants had infusion reactions. One participant received 8 mg/kg BMS-986253 monotherapy and experienced a grade 1 infusion reaction on Cycle 1 Day 1, which did not recur with subsequent infusions. Two participants treated with 2,400 mg BMS-986253 Q2W + 480 mg nivolumab Q4W experienced infusion reactions: one grade 2 infusion reaction on Cycle 1, Day 15 and continued to receive subsequent infusion of study therapy and tolerated well, and one experienced a grade 4 infusion reaction on Cycle 2, Day 15 that led to drug discontinuation.

Of note, there has been a higher-than-expected incidence of hemophagocytic lymphohistiocytosis (HLH) in participants receiving ipilimumab + nivolumab + blinded study drug (BMS-986253 or placebo) in Part 2 of Study CA027-002. As of 31 Jan 2023, 159 participants were treated in Part 1 with the nivolumab + BMS-986253 doublet, across different dose levels and/or schedules of BMS-986253. No dose-dependent toxicities were identified. In Part 1C, 15 participants were treated with BMS-986253 (3600 mg Q2W) in combination with nivolumab (1 mg/kg Q3W) and ipilimumab (3 mg/kg Q3W) to evaluate safety and preliminary anti-tumor activity of the triplet regimen. Part 2 was a randomized, double-blind evaluation of BMS-986253 (3600 mg Q2W) in combination with nivolumab (1 mg/kg Q3W) and ipilimumab (3 mg/kg Q3W) (Cohort 2A) vs nivolumab and ipilimumab plus placebo (Cohort 2B) in participants with melanoma that have progressed on anti-PD-(L)1 therapy with the objectives of comparing anti-tumor activity and assessing the safety of the triplet combination of BMS-986253 with nivolumab and ipilimumab. As of 27 Jan 2023, 57 participants across 18 sites in eight countries have been treated in the blinded part 2. To date, 3 HLH cases have been reported in Part 2, 2 of which were fatal. In Part 2, as of the data cutoff date of 10-Jan-2023, 54 participants with advanced/metastatic solid tumors have been treated with BMS-986253 3,600 mg or placebo Q2W in combination with nivolumab 1 mg/kg Q3W and ipilimumab 3 mg/kg Q3W.

The sponsor's safety monitoring team determined that the rate of HLH reported is higher than anticipated and elected to unblind the treatment assignment for the 3 participants to evaluate a potential contribution of BMS-986253. The randomization of the 3 participants with HLH was divided between the two arms. Of the 2 HLH cases with a fatal outcome, 1 occurred in each arm (2A and 2B). Overall, the incidence rates of HLH reported in the 2 arms were not considered meaningfully different. There were no HLH cases reported in participants treated with BMS-986253 in the following cohorts:

BMS-986253 monotherapy in phase 1 Study CA027-001 (n=15), BMS-986253 + nivolumab in CA027-002 Part 1A/B (n=144), nivolumab + ipilimumab + BMS-986253 in CA027-002 Part 1C (n=15), nor in participants (n=122) in 8 investigator sponsored research studies evaluating BMS-986253 in combination with nivolumab and other drugs in oncology indications.

[figure not shown]
In summary, it was determined that a contributory factor of BMS-986253 for the reported cases of HLH cannot be ascertained. The basis for the higher-than-expected frequency of HLH in the study cannot yet be determined and the evaluation is further confounded by the presence of significant comorbidities in the affected participants, including sepsis, possible gastrointestinal perforation, and viral infection (i.e., a recent COVID-19 infection in one participant, and evidence of EBV in 2 participants), all of which can present with an overlapping symptom complex and/or may contribute to the development of HLH. In addition, HLH case reports are a well described complication of immune checkpoint inhibitor monotherapy (pembrolizumab or nivolumab alone) or nivolumab/ipilimumab combinations. [98]

Because BMS-986253 is scheduled for intravenous (IV) administration, extravasation at the site of infusion may induce reactions such as edema, redness, itching, and tenderness. To date, no injection-site reactions have been reported.

1.2.4.2 Dosing

In a previous trial that enrolled non-cancer subjects noted above,[96] BMS-986253 was given as a single IV dose first at escalating dose levels ranging from 0.15 to 8 mg/kg. Subsequently, the same participants were treated with 4 weekly doses of 0.15 to 4 mg/kg. In the trial with advanced solid cancers as monotherapy,[97] BMS-986253 was given as a single IV dose first at escalating dose levels ranging from 4 to 32 mg/kg. Subsequently, the same participants were treated with the antibody every 2 weeks until progression with the same dose. In a currently ongoing trial that enrolled advanced cancer participants in combination with nivolumab at a dose of 480 mg every 4 weeks,[95] BMS-986253 is given as a single IV flat dose escalating from 600 to 2400 mg every 4 weeks and as a single IV flat dose escalating from 1200 to 2400 mg every 2 weeks. The last dosing regimen of 2400 mg every 2 weeks showed the best profile in terms of the deepest and most durable reduction of serum IL-8 levels among dose groups (Figure 2). Based on this, exploratory PK/PD modeling on serum IL-8 suggested that higher dose of BMS-986253 may further improve serum IL-8 suppression. Ongoing studies are currently testing higher dosing of 3600 mg every 2 weeks [Personal communication with BMS].

Figure 2. Flat dosing regimens and serum IL-8 levels in subjects treated with BMS-986253 in combination with nivolumab.

1.2.4.3 Pharmacokinetic and pharmacodynamic data

After single dose administration, the peak BMS-986253 serum concentration occurs at around 1 hour. Maximum plasma concentrations are dose-dependent, but plasma clearance rates are dose-independent. The half-life of the antibody is approximately 11.3 days. The pharmacodynamics effect was evaluated by measuring the IL-8 levels in wound fluid. In the three highest dose levels tested, there appeared to be a dose-dependent reduction in the IL-8 concentration in the wound fluid (2, 4, and 8 mg/kg).^[96] In the phase 1 dose escalation study as monotherapy,^[97] a sustained reduction in serum IL-8 > 50% was detected in 6 of 15 participants by assessing changes in serum IL-8 measured in samples obtained pre- and post-dose. Of the 6 participants exhibiting a sustained reduction in serum IL-8, four were from the 6-participant cohort dosed at 32 mg/kg, and one of each was from the 4- and 16-mg/kg 3-participant cohorts. In the ongoing phase 1/2a trial in advanced cancers in combination with nivolumab,^[95] Single Molecule Array (SIMOA) technology is being used to detect serum free IL-8 (IL-8 that is not bound to therapeutic antibody). The serum free IL-8 results (as of the data cut-off date 16-Jan-2020) for 76 participants who were treated with varying doses of BMS-986253 in combination with nivolumab 480 mg Q4W and all participants displayed a rapid decrease in free serum IL-8 (Cycle 1 Day 2). The data suggest that BMS-986253 decreases free serum IL-8 in a dose- and frequency-dependent manner and that the 2,400 mg Q2W dosing provides the deepest and most durable suppression of free serum IL-8, with modeling suggesting that higher dose of BMS-986253 may further improve serum IL-8 suppression.

1.2.5 Rationale for Myeloid Malignancy Program Investigation

In general, long term treatment outcomes for MDS participants are dismal. It is estimated that of every 100 MDS participants, four will be long-time survivors, with the rest of succumbing to either MDS- or treatment-related complications (67) or MDS-unrelated complications (29).^[3] There has been no progress in populations based studies in survival of MDS participants during last 2 decades.^[77] Novel approaches are needed which do not rely exclusively on cytotoxic therapy and/or intervene earlier in the course of the disease. Current clinical trials for participants with MDS enroll less than 5% of MDS participants.^[76] With better understanding of complex MDS pathophysiology, trials using combination treatments are emerging, especially for those ineligible for the HSCT, therefore representing an unmet need.^[11]

Since immune disturbance in MDS is common pathologic finding,^[101] and MDSCs have been found to induce myelodysplasia,^[60] with evidence of VEGF-independent neoangiogenesis and overexpression of EMT transcription factors as important processes in the evolution of MDS,^[53] there is a reasonable evidence that by blocking IL-8-mediated processes with IL-8 neutralization, a positive, disease-modifying therapeutic effect could be achieved. Preclinical *in vitro* work has also shown that blockade of the IL-8 receptor, CXCR2, led to significant reduction in the proliferation of several leukemic cell lines and primary AML/MDS cells. ^[37]

In the preclinical experiments done in Laboratory of Receptor Biology and Gene Expression (NCI/CCR), a heterozygous U2AF1 mutation was found to lead to widespread changes in translation such that mutant cells showed a ‘non-oncogene addiction’ to the ribosome biogenesis machinery.^[69] These data indicate an unanticipated functional connection between a splicing factor mutation and the ribosome biogenesis machinery. The preceding observations necessitate clinical correlates which specifically interrogate post-transcriptional regulation in MDS. Although there has been exhaustive DNA and RNA sequencing in MDS, there has been little if any quantitative measurements of translational regulation and this trial will allow a novel insight in the pathophysiology if MDS in synergy with the ongoing basic laboratory NCI/CCR research.

A new Clinical and Translational Correlates Facility was recently funded by the *FY20 Directors Challenge Innovation Award* and is physically housed initially within NHLBI space (PI [name] *et al*). This facility will create the ability to perform standardized research correlates proposed on this study and across the growing NIH Myeloid Malignancies Clinical Trials portfolio. Work from intramural investigators has recently demonstrated that high-sensitivity genomic measurements outperform conventional clinical assessments for myeloid malignancy participants in predicting relapse and survival following HSCT and suggest that additional intervention on high-risk subjects can improve clinical outcomes.^[102] This sets the stage for a “precision medicine” approach where personalized assessments of clonal disease burden can be used not only to judge the success of therapy, but also as a target for intervention.

In this trial we hypothesize that the addition of BMS-986253 to treatment with DNMTi is safe in adult MDS participants. Based on the presented data on IL-8 in MDS, we also hypothesize that IL-8 suppression with BMS-986253 will enhance efficacy of DNMTi therapy in adult HR-MDS participants and will be also effective for cytopenia-improvement as monotherapy in LR-MDS participants.

2 ELIGIBILITY ASSESSMENT AND ENROLLMENT

2.1 ELIGIBILITY CRITERIA

2.1.1 Inclusion Criteria

1. Participants must have histologically or cytologically confirmed MDS according to 2016 WHO criteria[1]
 - a. And:
2. have HR-MDS (R-IPSS ≥ 3.5) and received a minimum of 2 and maximum of 8 prior cycles for phase I and 4 for phase II of DNMTi therapy, or
3. have LR-MDS (R-IPSS <3.5),
 - a. and, at least one cytopenia:
 - i. granulocytes $< 1.0 \times 10^9/L$ and/or
 - ii. hemoglobin $< 110 \text{ g/L}$ with signs/symptoms of symptomatic anemia or transfusion-dependency
 - iii. platelets $< 100 \times 10^9/L$

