2.1.2 Exclusion Criteria

2.1.2.1 For phase I: Participants with HR-MDS (R-IPSS ≥ 3.5) that have not yet received or received less than 2 cycles of DNMTi therapy.

2.1.2.2 Participants with LR-MDS (R-IPSS < 3.5) with the following characteristics that have not yet received or are still deriving benefit from the following standard of care therapies:

- Hgb < 10 g/dL, Epo level < 500 mU/mL: Erythropoietin-stimulating agents (ESAs)
- MDS with del5q: Lenalidomide
- MDS with ringed sideroblasts (MDS-RS) with SF3B1 mutation: Luspatercept

2.1.2.3 Participants with platelet transfusion-refractory thrombocytopenia, with inability to keep platelet threshold above 10K/mcL with transfusions or those with ongoing or uncontrolled hemorrhagic complications.

2.1.2.4 Participants with clinically significant neutropenia, ANC < 100 , with frequent hospitalizations for infection (average > 1 hospitalization per month in past 6 months)

2.1.2.5 Participants who are receiving or have received any other investigational agents within 28 days before start of study treatment.

2.1.2.6 History of allergic reactions attributed to compounds of similar chemical or biologic composition to DNMTi or other agents used in study.

2.1.2.7 Uncontrolled intercurrent illness including, but not limited to, ongoing or active infection, symptomatic congestive heart failure, unstable angina pectoris, cardiac arrhythmia, or psychiatric illness/social situations that would limit compliance with study requirements.

2.1.2.8 Pregnant women or women presently breast-feeding their children are excluded due to unknown risks to a developing fetus or infant.

2.1.2.9 Any significant disease that, in the opinion of the investigator, may impair the participant's tolerance of study treatment.

2.1.2.10 Active or uncontrolled autoimmune diseases requiring treatment.

2.1.2.11 Chronic hepatitis B or C infection, because potential immune impairment caused by these disorders may diminish the effectiveness of this immunologic therapy.

2.1.2.12 HIV-positive participants are ineligible because of the potential for decreased immune response.

2.1.2.13 Presence of any other malignancy (except basal and squamous cell carcinoma of the skin, or stable chronic cancers on hormone or targeted therapy) for which participant received systemic anticancer treatment within 24 months prior to enrollment.

2.1.2.14 Prior history of allogeneic hematopoietic stem cell transplantation.

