3 STUDY IMPLEMENTATION

3.1 STUDY DESIGN

This study consists of two phases:

- Phase I: determination of OBD of BMS-986253 with and without DNMTi for HR- and LR-MDS cohorts, respectively, and
- Phase II: examining the efficacy of BMS-986253 with and without DNMTi for HR- and LR-MDS cohorts, respectively

In the Phase I, subjects will be enrolled to start treatment with BMS-986253 after a minimum of 2 cycles and up to initiation of an 8th cycle of DNMTi.

The safety endpoint will be DLT on D28. In addition, follow up for safety will be assessed 100 days after the last dose of treatment.

OBD will be the lowest tolerated dose level showing optimal biological activity, defined as maximal suppression of serum free IL-8 levels.

Participants enrolled on phase I will be treated at the corresponding BMS-986253 dose level until occurrence of disease progression, death, or unacceptable toxicity or until response assessment on C7D1 (maximum 6 cycles) if no evidence of clinical response. The participants will be followed up for overall, event- and progression-free survival until the study closure. The study will be closed when all enrolled participants have been followed up for at least 8 years or have died.

[figure not shown]
Both Phase I and II portions of study will enroll two cohorts:

A) HR-MDS: subjects with higher-risk MDS that will be treated with BMS-986253 in combination with DNMTi.

B) LR-MDS: subjects with lower-risk MDS that will be treated with BMS-986253 given as monotherapy.

In the Phase II portion, the treatment naïve subjects (or up to 4 cycles of prior DNMTi) will start treatment with BMS-986253 from the first cycle and the efficacy will be assessed until any off-treatment criteria are met (Section 3.8). BMS-986253 will be administered on days 1 and 15 of each cycle, and participants will remain on therapy until disease progression, death, or unacceptable toxicity or taken off therapy if no evidence of clinical response after 6 cycles (C7D1). The participants will be followed up for overall, event- and progression-free survival until the study closure. The study will be closed when all enrolled participants have been followed up for at least 5 years or have died.

Study treatment schema

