Survival	Endpoints: 
 Overall: death from any cause Event free: failure or death from any cause PFS: disease progression or death from MDS DFS: time to relapse Cause-specific death: death related to MDS

MDS, myelodysplastic syndromes; Hgb, hemoglobin; CR, complete remission; HI, hematologic improvement; PR, partial remission; FAB, French-American-British; AML, acute myeloid leukemia; PFS, progression-free survival; DFS, disease-free survival.

To convert hemoglobin from grams per deciliter to grams per liter, multiply grams per deciliter by 10.

*Dysplastic changes should consider the normal range of dysplastic changes.

†In some circumstances, protocol therapy may require the initiation of further treatment (eg, consolidation, maintenance) before the 4-week period. Such participants can be included in the response category into which they fit at the time the therapy is started. Transient cytopenias during repeated chemotherapy courses should not be considered as interrupting durability of response, as long as they recover to the improved counts of the previous course.

Hematologic Improvement

Category	Participant pre-trial baseline	Response criteria
----------	--------------------------------	-------------------

Erythroid response (HI-E)	No Transfusion Dependence at baseline (0 RBC transfusions in 16 weeks)	At least 2 consecutive Hgb measurements ≥ 1.5 g/dL for a period of minimum 8 weeks in an observation period of 16 to 24 weeks compared with the lowest mean of 2 Hgb measurements (apart from any transfusion) within 16 weeks before treatment onset; only a response duration of at least 16 weeks, however, is considered clinically meaningful
	Low Transfusion Dependence at baseline (3-7 RBC transfusions in 16 weeks in at least 2 transfusion episodes, maximum 3 in 8 weeks)	Transfusion independence, defined by the absence of any transfusions for at least 8 weeks in an observation period of 16-24 weeks with the same transfusion policy compared with 16 weeks prior to treatment; only a response duration of at least 16 weeks, however, is considered clinically meaningful

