10.3.2 Evaluable for objective response

Only those participants who have measurable disease present at baseline, have received at least one cycle of therapy with study drug, and have had their disease re-evaluated will be considered evaluable for response. These participants will have their response classified according to the definitions stated below. (Note: Participants who exhibit objective disease progression prior to the end of cycle 1 will also be considered evaluable.)

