17.6 APPENDIX F: CLINICAL DATA ELEMENTS FOR CRF ENTRY IN CLINICAL DATABASE

Patient (recipient) characteristics at protocol entry

- Sex (male, female)
- Age at enrollment (number)
- Ethnicity (white, black, American Indian/Alaskan native, Asian/Pacific islander, Hispanic, other)
- ECOG and Karnofsky performance status
- Diagnosis - MDS (high risk or low risk)
- 2016 WHO classification of MDS (MDS with single lineage dysplasia [MDS-SLD], MDS with ring sideroblasts and single lineage dysplasia [MDS-RS-SLD], MDS with ring sideroblasts and multilineage dysplasia [MDS-RS-MLD], MDS with multilineage dysplasia [MDS-MLD], MDS with excess blasts [MDS-EB], MDS with isolated del(5q), MDS unclassifiable [MDS-U],
- Date of MDS diagnosis (month, year)
- Age at MDS diagnosis
- Revised International Prognostic Scoring System (IPSS-R) score at MDS diagnosis
- Cytogenetic profile at diagnosis and enrollment, if available (see Appendix C)- only need overall score (very good, good, intermediate, poor, very poor)
- Bone marrow blasts %, if available
- Hemoglobin, if available
- Platelet count, if available
- Absolute neutrophil count (ANC), if available
- RBC transfusion dependance (transfusion dependent or independent)
- Platelet transfusion dependance (transfusion dependent or independent)
- Average # of transfusions per month (RBCs units and instances of platelets transfusions) in the 3 months leading up to baseline on study
- Laboratory values will be collected from time of screening for duration of trial
- TP53 mutation status at enrollment, if available (TP53 mutation positive or negative)
- Names and # of cycles of prior Lines of therapy for MDS.
- Response to most recent line of therapy: CR (complete response), PR (partial response), HI (hematologic improvement), mCR with HI (marrow CR with hematologic improvement), mCR without HI (marrow CR without hematologic improvement), SD (stable disease), PD (disease progression)
- MDS-CI (low risk, intermediate risk, high risk)
- Rockwood frailty index (see Clinical Frailty Scale)
- Disease status at time of enrollment: CR (complete response), PR (partial response), HI (hematologic improvement), mCR with HI (marrow CR with hematologic improvement), mCR without HI (marrow CR without hematologic improvement), SD (stable disease), PD (disease progression)
- Patient Reported Outcome Questionnaires (per section [3.5.3](#))
 - Subjects > 18 years of age:
 1. EORTC QLQC30 score (patient reported)- see questionnaire

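### A response that HR-MDS participants already had on prior DNMTi can count toward the primary ORR, because the plan neither excludes it nor ties the response reference to study entry

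*Combined protocol and SAP*

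**What the plan says.** **Entry.** Section 2.1.1 admits HR-MDS participants who "received a minimum of 2 and maximum of 8 prior cycles for phase I and 4 for phase II of DNMTi therapy". Section 3.1 describes phase II as "the treatment naïve subjects (or up to 4 cycles of prior DNMTi". These two statements differ on whether a minimum of 2 cycles applies in phase II and must be reconciled, but both allow pre-treated participants. For LR-MDS, section 2.1.1 requires a cytopenia, and section 2.1.2.2 excludes those "that have not yet received or are still deriving benefit from the following standard of care therapies". HR-MDS has neither condition. The R-IPSS threshold of 3.5 carries no time point, and Appendix F records the score at diagnosis. Appendix F also lists, as possible values, "Disease status at time of enrollment: CR (complete response), PR (partial response), HI (hematologic improvement), mCR with HI (marrow CR with hematologic improvement".

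**Counting.** Section 10.2 defines the primary response as CR, PR or marrow CR with HI. In section 6.3.1:
- CR is a set of absolute limits for marrow blasts, hemoglobin, platelets, neutrophils and peripheral blasts.
- PR and marrow CR need a blast fall of at least 50% over pretreatment, a term not tied to either drug.
- Erythroid HI in participants without transfusions is judged against hemoglobin "within 16 weeks before treatment onset". The transfusion-based rules also look back 16 weeks.

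Section 10.3.2 limits response evaluation: "Only those participants who have measurable disease present at baseline". The term is not defined for MDS. No section says how a response already present at enrollment is handled.

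**Pooling.** Stage 1 of the HR design includes 6 phase I participants treated at the OBD, provided they meet phase II eligibility (section 10.2). Phase I HR entry requires at least 2 prior DNMTi cycles (sections 2.1.1 and 2.1.2.1).

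**The concern.** The HR hypothesis in section 1.2.5 is that IL-8 suppression enhances the efficacy of DNMTi. In a single-arm trial, a response obtained on DNMTi before the first antibody dose carries no information on that, yet it can enter the numerator of the go/no-go rule (6 of 15, then 13 of 32). The error runs in one direction, toward go. It also affects time to best response, a secondary endpoint in section 10.4.3. The null rate of 30% rests on response rates in DNMTi-untreated participants, so it was not set for a cohort in which some enter already responding.

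**Working it through.** **1. Reproduce the design.** Inputs from section 10.2: n1 = 15, go if at least 6 respond; N = 32, success if at least 13 respond; p0 = 0.30, p1 = 0.50, alpha 0.10, beta 0.20.

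- P(early termination) = P(Bin(15, p) ≤ 5)
- P(success) = Σ over x = 6 to 15 of P(Bin(15, p) = x) × P(Bin(17, p) ≥ 13 − x)

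At p = 0.30, early termination is 0.7216 (plan: 72.2%) and the type I error 0.0997. At p = 0.50, power is 0.804. The stated design reproduces.

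**2. Which entry responses can be counted?**
- CR: no change from study entry is required, so a CR held from day 1 meets the definition at the first on-study marrow, unless the measurable-disease condition removes the participant.
- PR and marrow CR: if pretreatment means before DNMTi, an entry PR or marrow CR qualifies. If it means the marrow taken within 30 days before study treatment (sections 2.2.2.5 and 2.4), a further fall of at least 50% is needed.
- The HI part of marrow CR with HI: assuming 28-day prior cycles, 2 to 4 cycles last 56 to 112 days, that is 8 to 16 weeks of the 16-week look-back. A hemoglobin rise gained on DNMTi alone can then register as erythroid HI.

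**3. Size, unfavourable case.** Let f be the fraction entering in response and keeping it, with the rest responding at 0.30. The documents do not give f. The counted rate is f + 0.30(1 − f).

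| f (assumed) | counted rate | P(success), no antibody effect | P(early termination) |
|---|---|---|---|
| 0 | 0.300 | 0.100 | 0.722 |
| 5% | 0.335 | 0.192 | 0.613 |
| 10% | 0.370 | 0.317 | 0.499 |
| 15% | 0.405 | 0.460 | 0.388 |
| 20% | 0.440 | 0.604 | 0.287 |

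**4. Pooled participants only.** Suppose exactly 2 of the first 15 enter in response and all others respond at 0.30. Early termination becomes P(Bin(13, 0.30) ≤ 3) = 0.421, so the chance of passing stage 1 rises from 0.278 to 0.579, and the chance of false success from 0.10 to 0.24.

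**5. Favourable case.** If entry and later responses together total 30%, the counted rate is 0.30 and the false-success probability stays at 0.0997. The later null rate among those not in response at entry is then (0.30 − f)/(1 − f): 0.263 at f = 5%, 0.222 at 10% and 0.125 at 20%.

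**The case against.** A reader might infer that the plan credits every entry response to BMS-986253. The documents do not say that; they are silent. Several points limit the route:

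- Section 6.3 names a baseline marrow and then compares interim marrows with the pre-treatment examination. This suggests that the baseline marrow is the blast reference. On that reading an entry PR or marrow CR does not count without a further fall.
- HI alone is not a primary response, so the look-back matters only for someone who also meets marrow CR.
- On its face, the measurable-disease condition would remove a participant in CR.
- Scored at entry with Appendix C, CR-level blood counts contribute 0 points. With blasts below 5%, the total is then at most 2 for good and 3 for intermediate cytogenetics, both under 3.5. Only poor cytogenetics with blasts above 2%, or very poor cytogenetics, would reach the threshold.
- The Appendix F list of statuses is generic. It serves both cohorts and several time points, and does not show that such entrants are expected.
- The larger figures need generous assumptions. If half the cohort is pre-treated and 30% of those are in response, f = 15%. Giving the remainder a fresh 30% puts the pre-treated at 0.30 + 0.70 × 0.30 = 51% on DNMTi alone, just above the 20-50% range in section 10.2. If few pre-treated participants enroll, f could be near zero.
- The primary objective is ORR to the combination, and the null already allows for a DNMTi contribution.

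These points stand as limits on size and certainty. They do not close the gap: pretreatment, measurable disease and the timing of R-IPSS are all left open, and the primary conclusion should not rest on how they are read after the data are in. The allowance for DNMTi in the null covers responses expected in untreated participants, not selection of those already in response.

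**Conclusion.** The entry gap is established: nothing keeps HR-MDS participants who are responding to DNMTi out of phase II or out of the pooled phase I group. That such a response can count toward the primary ORR follows from the absolute CR limits as written, subject to the undefined measurable-disease condition. For PR and marrow CR with HI it is possible but depends on the reading. It would be too strong to say that earlier responses do count in all three categories, or that the true type I error is 0.32 or 0.60. Those figures belong to an assumed f of 10% or 20%, full persistence of the response and a fresh 30% rate in everyone else. Across the assumptions examined, with f up to 20%, the false-success probability runs from 0.10 (total response unchanged, attribution problem only) to 0.60. Because even 5% entry responders could nearly double the stated error and the remedy is small, the rule should be settled before stage 1 is evaluated.

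**What to change.** 1. In sections 6.3.1 and 10.3.2, set the reference for HR participants with prior DNMTi to the enrollment marrow for blasts and to on-study baseline counts for HI.
2. Count a participant enrolled in CR, PR or marrow CR with HI as a responder only on reaching a better category than the enrollment status, and write down the order of the categories. A participant already in CR is not evaluable for response. This also gives the measurable-disease condition a meaning for MDS.
3. Apply the same rule to the pooled phase I participants.
4. Report ORR separately by prior DNMTi exposure.
5. State when R-IPSS is scored for eligibility, and reconcile sections 2.1.1 and 3.1 on prior cycles in phase II.

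**Cost.** Appendix F already collects enrollment status. The reported ORR may be slightly lower and a few participants may need replacing. As an upper bound, if every entry responder were replaced, 32/(1 − f) gives 34, 36 and 40 treated at f = 5%, 10% and 20%. The 30% null should be re-checked for the pre-treated subset. Keeping 13 of 32 is conservative if the true null rate is lower: the chance of success with no effect would be 0.028 at 25% and 0.004 at 20%.
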